3.2 BELKYRA® TREATMENT

Subjects will undergo treatment with BELKYRA® injected into subcutaneous fat tissue in the submental area (Visit 2.1/Day 0) (note: Screening and Visit 2.1/Day 0 may occur the same day if all eligibility criteria are confirmed prior to treatment and the subject is not participating in the Biopsy Sub-study). Seven days after the initial BELKYRA® treatment (Visit 3.1), the subject will return to the clinic for a safety evaluation. Eight weeks after BELKYRA® treatment, the submental profile will be evaluated by the Investigator and subject. If the Investigator and subject agree that no further intervention is required to achieve the desired result, subjects may receive VOLUMA™ treatment (Visit 4). If further intervention is required to achieve the desired result, subjects may receive up to 5 optional BELKYRA® treatments (Visits 2.2 to 2.6). Optional BELKYRA® treatments will be

Clinical Study Protocol: CMO-MA-FAS-0513

administered at least 8 weeks apart, for a maximum of 6 treatments (including initial BELKYRA® treatment at Visit 2.1/Day 0). Subjects who receive optional BELKYRA® treatments will be contacted by telephone 7 days after each treatment for safety evaluation (Visits 3.2 to 3.6). Eight weeks after each BELKYRA® treatment, the submental profile will be assessed, as described above, and a decision made whether further BELKYRA® treatments are desired. When it is determined that further BELKYRA® intervention is not required or the maximum number (6) of BELKYRA® treatments have been administered, the subject receives VOLUMA™ treatment (Visit 4).

NOTE: Subjects participating in the Biopsy Sub-study will have an additional visit (Visit B2) between the final BELKYRA® treatment and the first VOLUMA™ treatment. See *Figure 3.1* and *Section 3.1: Biopsy Sub-Study*.

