9.1 DEFINITIONS

9.1.1 Adverse Events (AE)

9.1.1.1 Drug

An AE is any untoward medical occurrence in a subject administered a pharmaceutical product and that does not necessarily have a causal relationship with this treatment. An adverse event can therefore be any unfavorable and unintended sign (including an abnormal laboratory finding), symptom, or disease temporally associated with the use of a medicinal (investigational) product, whether or not related to the medicinal (investigational) product.

AEs will be assessed and documented, as appropriate, throughout the study (i.e., after informed consent has been obtained). At each visit, the Investigator will begin by querying for adverse events by asking each subject a general, non-directed question such as “How have you been feeling since the last visit?” Directed questioning and examination will then be done as appropriate. All reported adverse events will be documented on the AE eCRF.

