2.1 Study Design

This Phase IV trial is a prospective, open-label, multi-center, interventional, drug and medical device, post-marketing study. Each subject will act as his/her own control. Subjects will attend a minimum of 6 and maximum of 18 visits.

Approximately 50 male and female subjects will be treated. Approximately 10 of them are expected to participate in the Biopsy Sub-study.

All subjects will sign an informed consent form (ICF) at the Screening Visit (Visit 1). Eligible subjects will undergo treatment with BELKYRA injected into subcutaneous pre-platysma fat tissue in the submental area (Visit 2.1/Day 0). Seven days after the initial BELKYRA treatment (Visit 3.1), the subject will return to the clinic for a safety evaluation. Eight weeks after BELKYRA treatment, the submental profile will be evaluated by the investigator and the subject. If further BELKYRA intervention is required to achieve the desired result, subjects may receive up to 5 optional BELKYRA treatments (Visits 2.2 to 2.6), for a maximum of 6 treatments including the initial required treatment. Subjects who receive optional BELKYRA treatments will be contacted by telephone 7 days after treatment for safety evaluation (Visits 3.2 to 3.6). The submental profile will be assessed as described 8 weeks after each BELKYRA treatment, and a decision made if further BELKYRA treatments are desired.

When the investigator and the subject agree that no further BELKYRA intervention is required to achieve the desired result, the subject may receive VOLUMA treatment (Visit 4). Fourteen days after VOLUMA treatment, subjects will return to the clinic (Visit 5) and the investigator will assess whether a VOLUMA touch up treatment is to be performed. All subjects will attend a final exit visit (Visit 6) which is 4 weeks after the last VOLUMA treatment (Visit 4 if no touch-up done or Visit 5, if touch-up was performed).

Subjects will have the option of participating in a Biopsy Sub-study. Participation in the sub-study is voluntary and will not affect the subject's eligibility to participate in the main study. Biopsy samples will be collected from the submental region at 2 time points: Visit B1 will occur at least 4 weeks before the first BELKYRA treatment (at Visit 2.1); Visit B2 will occur 8 weeks after the last BELKYRA treatment and at least 4 weeks prior to VOLUMA treatment (at Visit 4). Histological changes from baseline to after final BELKYRA treatment(s) will be evaluated.

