6.3 SubGroup Analyses

As males and females may have differing expectations and perceptions of aesthetic improvement, assessment outcomes of efficacy data will be analyzed by gender.

7. Safety Analyses

All safety analyses will be based on the safety population. Safety will be assessed primarily in terms of the frequency count and the binominal incidence rate of the AEs of interest. The binomial incidence rate for a given event of interest during a certain period is defined as the number of unique patients who have experienced the event of interest in the period divided by the number of patients in the safety population, then multiplied by 100. Note that, for the calculation of the incidence rate, the numerator will be counted at subject level. Specifically, if a subject has experienced the event(s) of interest (at a given summarization level) more than once during the period, he/she will be counted only once into the numerator. The total number of events will also be presented. The 95% confidence intervals (CIs) for binomial incidence rate per the Clopper and Pearson exact method (via SAS procedure Proc Freq) will also be calculated and presented.

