7.2 Adverse Events

Adverse events (AE) will be coded using MedDRA v20.1 or later to give a PT and a SOC term for each event.

An AE is defined as any untoward medical occurrence in a clinical investigational patient administered a pharmaceutical (investigational) product or any undesirable physical, psychological or behavioral effect experienced by a subject during his/her participation in a study, in conjunction with the use of the device and which does not necessarily have to have a causal relationship with this treatment.

All AEs will be included in by-subject AE listings. A separate listing will be created with all the distinct levels of SOC and PT, and the verbatim investigator description reported in the study. Sorting will be by earliest observed SOC, PT within SOC and then verbatim description.

A treatment-emergent adverse event (TEAE) is a post-baseline AE where (i) there is no pre-treatment AE of the same MedDRA primary SOC and PT; or (ii) the maximum severity during the post-baseline period is greater than the maximal severity of any pre-treatment AE of the same MedDRA primary SOC and PT during the enrollment visit. Note that the post-baseline period of the study starts upon the initiation of the BELKYRA treatment at Visit 2.1/Day 0.

Partial or missing AE start dates will be handled as per Section 3.3.3.1.

An overall summary of frequency count and the binomial incidence rate with associated 95% CIs will be presented to describe the incidents of TEAEs. Note that 95% CIs of the binomial incidence rate will be presented for the overall summary analyses of TEAEs, but not for the by-visit analyses. Percentages and corresponding 95% CIs will be displayed to 1 decimal place.

Each type of AE will be tabulated by SOC and PT within SOC. The SOC and PT within SOC will be sorted by descending frequency. Number of subjects with percentage and number of events will be presented based on SOC and PT.

The incidence of all TEAEs by SOC and PT will be presented for the following categories:

- Any TEAE
- Any TEAE related to BELKYRA
- Any TEAE related to VOLUMA
- Any TEAE related to anesthesia
- Any TEAE related to study procedure
- Any TEAE related to BELKYRA/VOLUMA and leading to discontinuation of treatment with BELKYRA/VOLUMA
- Any TEAE by maximum severity

The following listing will be provided:

- Listing of all TEAE

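### By-visit safety rates divided by the whole safety population fall as fewer subjects reach BELKYRA sessions 2 to 6, even if the risk per session does not

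*SAP*

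**What the plan says.** **Rate.** The opening of SAP Section 7 defines a binomial incidence rate for an event during a given period. The number of distinct subjects with the event is "divided by the number of patients in the safety population" and multiplied by 100. SAP 3.1 defines that population as all who consented, including subjects who were biopsied but never received BELKYRA.

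**By-visit analyses.** SAP 7.2 states that confidence intervals are "presented for the overall summary analyses of TEAEs, but not for the by-visit analyses". SAP 7.3 has a matching sentence for SAEs. Neither section says how an event is assigned to a visit or gives a separate denominator.

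**Who reaches later sessions.** Protocol 3.2 makes BELKYRA treatments 2 to 6 optional. They depend on the judgement, 8 weeks after each treatment, that more is needed.

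**How day 7 is checked.** Protocol 3.2, on session 1: "Seven days after the initial BELKYRA® treatment (Visit 3.1), the subject will return to the clinic for a safety evaluation". After an optional session, subjects are instead "contacted by telephone 7 days after each treatment for safety evaluation (Visits 3.2 to 3.6". SAP 2.1 describes the same arrangement. On method, Protocol 9.1.1.1 says: "At each visit, the Investigator will begin by querying for adverse events by asking each subject a general, non-directed question", and then: "Directed questioning and examination will then be done as appropriate".

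**The concern.** A rate for session 3 should describe the subjects who had session 3. A subject who stopped after session 1 cannot have a reaction to session 3, but still counts in the denominator under the Section 7 rule. The rate therefore mixes two things: the risk among those treated, and the share of the safety population that was treated at all.

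Up to six BELKYRA sessions are allowed, so a reader of a by-visit table will look for whether reactions ease or build up with repetition. Under this rule the table can slope downward when the risk per session is flat, and also when it is rising. Local harm that accumulates with repeat treatment could then be missed.

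The change in day-7 contact mode is a second reason why session 1 and later sessions may not compare like with like for non-serious events. Neither document mentions it as a limitation.

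**Working it through.** The documents give no adverse event rates, no expected number of sessions and no figure for telephone ascertainment. There is no plan figure to reproduce, and the risk, continuation and capture values below are assumptions.

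**1. Denominator effect.**
Let N be the safety population, k the number who receive a given session, and r the risk among those treated. The rate under SAP 7 is r × k/N; the rate per treated subject is r. The ceiling of the SAP rate, reached if every treated subject has an event, is k/N.

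Take N = 50, the planned number treated. This is generous to the rule, because SAP 3.1 counts all who consented, so N can be larger. Assume r = 60% at every session, with perfect detection.

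| Treated at the session (k) | Rate per treated subject | SAP rate, 0.60 × k/50 | Ceiling, k/50 |
|---|---|---|---|
| 50 | 60% | 60% | 100% |
| 30 | 60% | 36% | 60% |
| 20 | 60% | 24% | 40% |
| 10 | 60% | 12% | 20% |
| 5 | 60% | 6% | 10% |

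**2. Rising risk.**
For the SAP rate to stay at 60% with 30 treated, the true risk would have to be 0.60 × 50/30 = 100%. Any rise from 60% that stops short of 100% would be tabulated as a fall. With 10 treated, the required risk would be 0.60 × 50/10 = 300%, which is impossible.

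**3. Contact-mode effect.**
Let s be the share of events found by telephone relative to a clinic check, and c the share of missed events recovered at the visit about 8 weeks later. At equal true risk, the ratio of later-session to first-session observed risk is s + (1 − s)c.

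- s = 0.90: 0.90 if c = 0; 0.95 if c = 0.5; 1.00 if c = 1.
- s = 0.75: 0.75 if c = 0; 0.875 if c = 0.5; 1.00 if c = 1.
- s = 0.50: 0.50 if c = 0; 0.75 if c = 0.5; 1.00 if c = 1.

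The effect runs from a halving to nothing, and the documents do not narrow it.

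**4. Relative size.**
Assume that 60% continue after each session, so that 50 × 0.6⁵ = 3.9 subjects reach session 6. The denominator alone takes the tabulated rate to 0.60 × 0.6⁵ = 4.7%. If later checks also capture only 70% to 85% of events, this becomes 4.7% × 0.70 = 3.3% to 4.7% × 0.85 = 4.0%. The denominator accounts for 60 − 4.7 = 55.3 points of the fall, and contact mode for a further 0.7 to 1.4.

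Once the denominator is corrected, the same capture range would give 0.60 × 0.70 = 42% to 0.60 × 0.85 = 51% at later sessions, against 60% at session 1. That is why contact mode still needs a footnote.

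**The case against.** **The by-visit tables are barely planned.** They appear only in notes on confidence intervals and in neither list of TEAE or SAE tables. No first-versus-repeat comparison is stated, Protocol 10.5.5 presents summary tables by study drug, and the SAP's table shells are not available to check. This is fair, and it means the exact layout is unknown. It does not remove the point, because a table left undefined falls back on the rule that Section 7 does state.

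**SAP 3.3.5 already uses subjects at risk as denominator.** It does, but only where nothing else is specified. Section 7 specifies something else, and does so for events within a period. Read as written, the Section 7 rule governs.

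**Other outputs limit the damage.** Event totals accompany the rates, session counts and volumes are summarised, and all TEAEs are listed. A careful reader could rebuild the right rate from these, but the printed percentage would still be wrong for its apparent purpose.

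**A stronger reading is tempting: that telephone follow-up will itself make repeat treatment look safer.** The documents do not support this.
- No readable passage makes an examination a fixed part of Visit 3.1. Protocol 9.1.1.1 leaves examination to judgement, and the visit-by-visit procedures are redacted.
- Directed questioning can be done by telephone, and subjects can notice many local reactions themselves.
- The submental profile is assessed 8 weeks after every session, which gives a later opportunity to pick up events.
- Nothing suggests that SAEs would be missed. Protocol 9.3 requires them to be notified within 24 hours.

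What stands is that an examination is possible in clinic and impossible by telephone, and that no diary covers the BELKYRA sessions, since the ISR Diary is for VOLUMA only. The direction of any bias is plausible; its size is not known.

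**Conclusion.** The point holds for the denominator. If the Section 7 rule is applied to by-visit TEAE and SAE tables, a later session's rate cannot exceed k/N, and it falls in proportion to the number treated when risk is constant. The figures of 36%, 12% and 6% rest on the assumed 60% risk, N = 50, and 30, 10 or 5 subjects treated. The proportional fall itself needs only that fewer subjects reach later sessions, which the optional design makes very likely.

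Contact mode is a secondary, unquantified reason not to read session 1 against later sessions for non-serious TEAEs. A reader might infer that it drives the decline; the working shows that it need contribute almost nothing.

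The primary endpoint is untouched, and whole-study TEAE incidence is not affected by the shrinking number treated. The change should be made, but the main efficacy conclusion does not depend on it.

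**What to change.** In SAP 7, 7.2 and 7.3:

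- Replace the by-visit analyses with tables by BELKYRA session. Assign to session k the events with onset from that session until the next study treatment (or study exit, if there is none).
- Use the subjects who received session k as denominator in place of the safety population, and print that number in each row. Keep the safety population for whole-study incidence.
- Add a footnote to the TEAE table that the day-7 safety evaluation is in clinic after session 1 and by telephone after sessions 2 to 6, so session 1 rates should not be read against later ones.

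This takes no position on how the day-7 checks should be conducted. The cost is SAP wording and a table shell, with no new visits or data, and SAP Section 1 allows amendments before database lock. The downside is that later-session rows will rest on few subjects and show less favourable percentages than the current rule would. Subjects who continue are also selected by need for further treatment, so the table remains descriptive.

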10.5.5 Adverse Events

AEs will be coded using MedDRA version 17.0 or higher, and presented by system organ class and preferred term. Treatment-emergent AEs will also be summarized by SAEs, AE severity, AE leading to treatment or study early termination, and relationship to study drugs/devices. Summary tables will be presented by the study treatment drug.

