6.2.1 Primary Efficacy Analysis16

6.2.2 Secondary Efficacy Analyses16

[REDACTED]

6.3 SubGroup Analyses 19

7. Safety Analyses.....19

7.1 Exposure to Study Treatment(s)..... 19

7.2 Adverse Events 20

7.3 Serious Adverse Events 21

7.4 Other Safety Analysis..... 22

7.5 Pregnancy 22

7.6 Subgroup Analyses for Safety Variables 22

8. Pharmacokinetic, Biomarker, Genomic, or Immunogenicity Data Analyses
.....22

9. Health Outcomes Data Analyses22

10. Interim Analyses22

11. Data Collected but not Analyzed.....23

12. References.....23

13. Appendices24

Summary of Changes

Version Number	Version Date	Author	Changes Made
1.0	14-Jan-2019	[REDACTED]	Initial Version
2.0	29-Aug-2019	[REDACTED]	Changes from V1.0 to V2.0 include: 
 • Revisions to section 6.2.3.3 - Image Analysis • Revisions to section 7.4 - Other Safety Analysis • [REDACTED]
3.0	21-Feb2020	[REDACTED]	Changes from V2.0 to V3.0 include: 
 • Addition of section 6.3 - SubGroup Analyses • [REDACTED]

1. Introduction

The purpose of this Statistical Analysis Plan (SAP) is to provide details of the data analyses as outlined in the study protocol dated on March 21, 2018 and titled “A Prospective, Open-label Study to Evaluate Sequential Treatment with BELKYRA® and Juvéderm® VOLUMA with Lidocaine (VOLUMA) for Overall Improvement in Jawline Contour”.

This SAP should be reviewed in conjunction with the study protocol. In case of any discrepancies in the statistics section between the protocol and the SAP, the SAP will supersede the protocol, as the SAP is intended to be more precise and specific. Any amendment to the SAP will be made prior to database lock. Any additional analyses performed but not described in the final SAP or deviations from the final SAP will be documented in the clinical study report.

This study is a Phase IV, post-marketing study sponsored by Allergan. It is a prospective, open-label, multi-center, interventional, drug and medical device study to evaluate the combined effectiveness of sequential BELKYRA treatments of convexity or fullness associated with submental fat and VOLUMA to restore volume along the mandible in enhancing the overall contour of the jawline. This post-marketing study includes an exploratory endpoint for a Biopsy Sub-study to evaluate histological changes from baseline to after the final BELKYRA treatment.

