4.2 Disposition and Withdrawals

The number of subject enrolled and the number and percentage of subjects completed and discontinued together with the reasons for discontinuation will be summarized for FAS. The number and percentage of subjects included, and reasons for exclusion, from each of the analysis sets will be presented as well.

Subject disposition (including date of and reasons for early discontinuation from study) will be listed for the FAS.

5. Demographics and Other Baseline Characteristics

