7.3 Serious Adverse Events

A serious adverse event (SAE) is any AE occurring at any dose that results in any of the following outcomes: death, a life-threatening AE, inpatient hospitalization or prolongation of existing hospitalization, a persistent or significant disability/incapacity, or a congenital anomaly/birth defect. While an unanticipated adverse device effect (UADE) is any device-related SAE that meets one or more of the criteria listed in the Sec. 9.1.3 of the Protocol in page 49.

An overall summary of frequency count and the binomial incidence rate with associated 95% CIs will be presented to describe the incidents of treatment emergent SAEs. Note that 95% CIs presented are for the overall summary analyses of SAE, but not for the by-visit analyses. Percentages and corresponding 95% CIs will be displayed to 1 decimal place.

The incidence of all treatment-emergent SAEs by SOC and PT within SOC will be presented for the following categories:

- Any SAE
- Any SAE related to BELKYRA
- Any SAE related to VOLUMA
- Any SAE related to anesthesia
- Any SAE related to study procedure

- Any SAE related to BELKYRA/VOLUMA treatment and leading to discontinuation of treatment
- Any SAE by maximum severity

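### The SAP tabulates adverse events leading to discontinuation only if related to a study product, which is narrower than the protocol, so that row may be understated

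*SAP*

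**What the plan says.** Protocol 10.5.5 commits to this: "Treatment-emergent AEs will also be summarized by SAEs, AE severity, AE leading to treatment or study early termination, and relationship to study drugs/devices". Relationship is a separate item in that list. It is not a condition on the discontinuation item, which covers both treatment and study.

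SAP 7.2 lists the TEAE categories to be tabulated by system organ class (SOC) and preferred term (PT). The only one about discontinuation is "Any TEAE related to BELKYRA/VOLUMA and leading to discontinuation of treatment with BELKYRA/VOLUMA". SAP 7.3 has the parallel entry for serious events: "Any SAE related to BELKYRA/VOLUMA treatment and leading to discontinuation of treatment". Both sections treat relation to anesthesia and relation to study procedure as categories distinct from relation to BELKYRA or VOLUMA.

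SAP Section 1 settles conflicts between the statistical sections: "the SAP will supersede the protocol, as the SAP is intended to be more precise and specific". The visible SAP text gives no reason for the narrower category; parts of the SAP are redacted.

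Three other outputs bear on the point. SAP 4.2 has subjects who "discontinued together with the reasons for discontinuation will be summarized for FAS". SAP 7.2 tabulates TEAEs of any cause, and it provides a "Listing of all TEAE".

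**The concern.** Two restrictions separate the SAP row from the protocol commitment: a relatedness filter, and the loss of study termination as an outcome. Because the SAP takes precedence, the table described in the protocol would not be produced as described.

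The filter depends on a causality judgment by the investigator (Protocol 9.1.5) in an open-label, single-arm study (Protocol 5.1.3), so no control arm is available to check attribution. The count also helps in reading the efficacy result. The primary analysis uses the Evaluable Set, which requires both products and a Visit 6 assessment (SAP 3.1 and 6.2.1). Subjects who stop before VOLUMA leave that analysis, and Protocol 10.7 allows for 20% dropping out or not going on to VOLUMA, that is 0.20 × 50 = 10 subjects. A reader will want to know how many of those losses were due to adverse events of any cause.

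**Working it through.** **1. The two texts side by side**

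| | Protocol 10.5.5 | SAP 7.2 and 7.3 |
|---|---|---|
| Cause | No condition | Related to BELKYRA or VOLUMA |
| What ends | Treatment or study | Treatment |

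**2. Which events fall outside the SAP row**

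- A TEAE judged unrelated that ends treatment or participation: omitted.
- A TEAE related only to anesthesia or to a procedure, for example the Visit B2 biopsy, that ends treatment or participation: omitted.
- A product-related TEAE that ends study participation: the row names treatment only. The SAP does not say whether leaving the study counts as stopping treatment.
- An event from the Visit B1 biopsy that begins and ends before Day 0: not a TEAE under SAP 7.2, so it belongs in neither the current row nor an all-cause TEAE row.

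**3. Whether another output supplies the same figure**

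- SAP 4.2 gives reasons for leaving the study, not AE terms. It is not stated to show a subject whose further BELKYRA or touch-up was stopped by an adverse event but who reached Visit 6.
- The table of TEAEs of any cause does not separate those that ended treatment.
- The TEAE listing gives no rate, and the SAP does not state that it flags discontinuation.

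**4. Size**

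The plan gives no figure for discontinuation due to adverse events, so there is none to reproduce. The treated number comes from Protocol 10.7: 40 / (1 − 0.20) = 50. The SAP's denominator is the safety population (SAP Section 7), which SAP 3.1 defines by consent, so it may exceed 50. I use N = 50, and N = 60 as an assumed larger value.

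Let r be the number of subjects with a related TEAE that ended treatment. Let u be the number of further subjects whose only discontinuing TEAEs are not related to either product.

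- SAP row: r / N
- All-cause row: (r + u) / N
- Shortfall: u / N, which is never negative and is zero when u = 0

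Per omitted subject this is 1/50 = 2.0 points, or 1/60 = 1.7 points.

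Intervals use the Clopper-Pearson method named in SAP Section 7: lower limit = Beta quantile 0.025 with parameters (x, N − x + 1); upper limit = Beta quantile 0.975 with parameters (x + 1, N − x). For x = 0 and N = 50 the upper limit is 1 − 0.025^(1/50) = 7.1%. The values of r and u below are assumptions.

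| N | r | u | Related only, % (95% CI) | All cause, % (95% CI) |
|---|---|---|---|---|
| 50 | 0 | 0 | 0.0 (0.0–7.1) | 0.0 (0.0–7.1) |
| 50 | 0 | 1 | 0.0 (0.0–7.1) | 2.0 (0.1–10.6) |
| 50 | 0 | 2 | 0.0 (0.0–7.1) | 4.0 (0.5–13.7) |
| 50 | 1 | 3 | 2.0 (0.1–10.6) | 8.0 (2.2–19.2) |
| 60 | 0 | 2 | 0.0 (0.0–6.0) | 3.3 (0.4–11.5) |

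**The case against.** The strongest reply is that little is hidden. Events outside the row are still counted in the any-cause TEAE table and, where they apply, in the anesthesia and procedure tables, and all are listed. Study exits are summarised with reasons and without a relatedness filter. A subject who forgoes VOLUMA by agreement after BELKYRA is treated as an early discontinuation (Protocol 3.3) and so enters the disposition summary. Repeat BELKYRA sessions and the touch-up are optional, so not receiving one is not clearly a discontinuation. Deciding that an event led to stopping is itself a site judgment.

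Most of this stands, and it limits the point. A reader might infer that the trial's tolerability result as a whole is understated, or that AE-driven exits go unreported. The documents support neither: TEAE incidence does not change, and exits can appear under SAP 4.2 if adverse event is one of the recorded reasons. A reader might also infer that all biopsy-related events are lost because of this row. Events confined to the period between Visit B1 and Day 0 are outside any TEAE table by definition, so only the Visit B2 biopsy is a fair example.

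The reply does not restore what the protocol described. No output is stated to give all-cause TEAEs leading to discontinuation by SOC and PT with a rate, and the SAP row narrows the protocol's commitment without a visible reason.

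**Conclusion.** The discrepancy between Protocol 10.5.5 and SAP 7.2 and 7.3 is real and does not depend on the data. Its effect does. The discontinuation row may be understated, and is so only if at least one subject stops treatment or participation because of a TEAE not judged related to BELKYRA or VOLUMA, or if product-related exits from the study are not counted as stopping treatment. The size is about 2 percentage points per omitted subject with a safety population of about 50, and less with a larger one. The documents give no basis for estimating how many such subjects there will be, and none is possible. The point concerns one descriptive safety row in each of the two sections; the primary endpoint is not affected.

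**What to change.** In SAP 7.2 and 7.3, add rows for any TEAE (and any serious TEAE) leading to discontinuation of BELKYRA, of VOLUMA, and of the study, regardless of relationship. Keep the existing related-only row as a subset. State what counts as discontinuation of each product, given that later BELKYRA sessions and the touch-up are optional. If the sponsor prefers the narrower row, the SAP should record the departure from Protocol 10.5.5 and give the reason.

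The cost is a few table rows and possibly a slightly higher reported rate. The existing row already requires each event to be classified by whether it ended treatment, so the treatment rows only drop a condition. Withdrawal date and reason are already recorded on the eCRF (Protocol 8.2). The study row also needs the exit linked to a specific event, which should be confirmed. SAP Section 1 allows amendment up to database lock; after that, the rows can be added as additional analyses documented in the clinical study report.
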